2.3 Individual protocol deviations

As this is a non-interventional study deviations from procedures set out in the study protocol will not necessarily lead to exclusions from analysis populations.

However, violations of important in- or exclusion criteria (e.g. no confirmed von Willebrand disease) or treatment schedule (e.g. prophylactic instead of on-demand treatment) are considered important as they may affect the reliability of analysis results.

The decision about the classification of individual protocol deviations and their consequences regarding assignment of subjects to analysis sets will be made during a data review meeting (DRM). A complete listing of protocol deviations and the judgment for assessment of subject disposition will be approved by the Sponsor and signed before database lock. All deviations along with the disposition of each subject will be recorded in a separate database member that will become part of the study database.

3 ANALYSIS POPULATIONS

The disposition of patients will be displayed according to the following analysis populations:

- Full Analysis set (FAS)
- Per-Protocol (PP) set
- Surgery (SURG) set

Membership of subjects will be decided upon in a DRM with the Sponsor before database lock. The proper flags for analysis sets exclusion (e.g., exclusion from PP set), will be included in the analysis dataset. The protocol deviation list should be finalized before database lock.

3.1 Full Analysis Set

The **full analysis (FAS) set** defined according to the intention-to-treat (ITT) principle will include all enrolled subjects.

3.2 Per Protocol Set

The **per-protocol (PP) set** is a subset of the FAS that will exclude subjects with important protocol deviations which may have an impact on the evaluation of the primary study outcome parameter.

3.3 Surgery Set

The **surgery (SURG) set** will be a subset of the FAS, containing all subjects who underwent a surgical procedure treated with any VCP prior to start of surgery.

Statistical Analysis Plan	Version 3.0		Page 8 of 17
Sponsor	Octapharma	Protocol No	WIL-29

3.4 Subgroup analyses

The analyses of the efficacy endpoints ‘total annualized bleeding rate (TABR)’ and ‘spontaneous annualized bleeding rate (SABR)’ will be presented in the following subgroups:

- Age groups (‘6 to 11, 12 to 16 and ≥ 16 years’).
- VWD type (‘severe type 1’, ‘type 2’ and ‘type 3’)
- Sex (‘Female’, ‘Male’)

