## 8.3 STUDY POPULATION

### 8.3.1 Number of Patients

Overall, around 55 PTPs aged  $\geq 5.5$  years at the time of enrolment will be included into this NIS. Of the 55 patients, at least 6 patients should have type 3 VWD and at least 6 patients should be  $\geq 5.5$  to  $< 16$  years of age.

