### 8.3.2 Inclusion Criteria

Patients who meet all of the following criteria are eligible for the study:

1. Male or female patients aged  $\geq 5.5$  years at the time of enrolment
2. VWD type 1 (baseline von Willebrand factor activity [VWF:RCo],  $< 30$  IU/dL), 2A, 2B, 2M, or 3 according to medical history requiring substitution therapy with a VWF-containing product to control bleeding
3. Currently receiving frequent on-demand treatment with a VWF-containing product
4. In female patients of child-bearing potential using hormonal contraception, the medication class should remain unchanged for the duration of their study participation
5. Voluntarily given, fully informed written and signed consent obtained before collection of any patient data

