1.4 Planned sample size

No formal sample size calculations were performed. The sample size of 55 patients was chosen based on feasibility and to allow data summaries to be produced. However, with a sample size of 55, a two-sided 95% confidence interval for the mean ABR will extend ± 0.8 from the observed mean, assuming that the standard deviation is 3 or less and the confidence interval is based on the large sample z statistic.

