4.2 Demographic and other background data

The disposition of subjects (cf. Section 3) will be tabulated for the entire population. Details on important protocol deviations will be listed.

Discontinued subjects will be described by frequency distributions including the reasons and in individual listings.

Demographic data (age, weight, height, BMI, ethnic group) will be summarized in tables and presented for the FAS population. Other baseline and background data as listed below will also be analyzed by descriptive tables (according to their type /continuous/categorical) for the FAS population:

- AB0 blood group (if available)
- Age at first treatment with VCP
- Family history of VWD
- History of VWD or FVIII inhibitors
- Available historical data on VWF activity obtained by VWF:RCo, VWF:Gp1bM, VWF:Gp1bR assays, or any other method and VWF:Ag as well as VWF multimer pattern for VWD type 2A, genotype for VWD type 2B, VWF multimer pattern for VWD type 2A, and genotype for VWD type 2B
- Historical annual bleeding rate (ABR) calculated from number of bleeding episodes in the previous 6 months

Statistical Analysis Plan	Version 3.0		Page 10 of 17
Sponsor	Octapharma	Protocol No	WIL-29

- Hemophilia Joint Health Score (HJHS) at baseline
- QoL scales (PROMIS-29, SF-36; SF-10 for patients <16 years of age) at baseline
- Historical PBAC score

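### The SAP's age groups for TABR and SABR overlap at 16 and leave eligible children aged 5.5 to under 6 without a group

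*SAP*

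**What the plan says.** SAP 3.4 states that the TABR and SABR analyses "will be presented in the following subgroups", and gives the age groups as "6 to 11, 12 to 16 and ≥ 16 years".

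Four other places bear on this:

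- Protocol 8.3.2 sets eligibility as "Male or female patients aged $\geq 5.5$ years at the time of enrolment", with no upper limit.
- Protocol 8.3.1 sets a recruitment minimum: "at least 6 patients should be $\geq 5.5$ to $< 16$ years of age".
- SAP 3.1 says the full analysis set "will include all enrolled subjects".
- SAP 4.2 divides patients at 16 for quality of life: "SF-10 for patients <16 years of age". Protocol 8.2.2 and 8.5.8 use the same cut at 16 for the choice of questionnaire.

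Neither the conventions in SAP 4.1 nor the derivation table in SAP 6.1 has a rule for age. SAP 2.2, on deviations from the protocol, deals only with surgery periods.

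**The concern.** A subgroup table of the primary endpoint should place each patient of the analysis set in exactly one row. Two things on the face of the text prevent that. The middle and upper groups both contain age 16, and the lowest group starts at 6 although enrolment starts at 5.5.

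If patients of these ages enrol and the labels are programmed as written, a patient can be counted twice or dropped, and the group sizes need not add up to the full analysis set. The two lower groups also do not add up to the band from 5.5 to under 16, which is the only age band with a recruitment target. Few patients under 16 are required, so one patient can be a visible share of a paediatric row.

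**Working it through.** **The plan's own figure.** SAP 1.4 gives a 95% half-width of ±0.8 for the mean bleeding rate in 55 patients, using a z-based interval and an SD of at most 3. Check: 1.96 × 3 / √55 = 0.793, which rounds to 0.8. It reproduces. It concerns the overall mean and does not depend on the age groups.

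**Do the groups partition the eligible ages?** Each age from 5.5 upward was assigned to the three groups as written, under each way of deriving age:

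| Age convention | Ages in no group | Ages in two groups |
|---|---|---|
| Completed years | 5.5 to <6 | 16.0 to <17 |
| Exact (decimal) age | 5.5 to <6, and between 11 and 12 | exactly 16.0 |
| Rounded to nearest year | none | 15.5 to <16.5 (all recorded as 16) |

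No convention gives a partition. Rounding to the nearest year closes the gap below 6 but keeps the overlap, and neither document states such a rule.

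**Effect on the counts.** Take completed years, with k patients aged 16 and m aged 5.5 to <6. The group sizes then sum to N + k − m, where N is the size of the full analysis set. With one of each (k = m = 1) and N = 55, the sum is 55 + 1 − 1 = 55. The total looks right although one patient is counted twice and another is missing.

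**Size of an omission.** If one child aged 5.5 to <6 enrols, the share of under-16 patients missing from the age table is:

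- 6 patients under 16 (protocol minimum): 1/6 = 17%
- 10 patients (assumed): 1/10 = 10%
- 15 patients (assumed): 1/15 = 7%

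**Size of a double count.** Suppose one 16-year-old joins a 12 to <16 group of n patients, and that patient's rate lies 3 bleeds per year from the group mean (one SD at the SAP's value). The mean moves by 3/(n + 1). For comparison, the t-based 95% half-width of the group mean at SD 3 is t(0.975, n−1) × 3/√n. The group sizes are assumed.

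| n | Shift in mean | 95% half-width |
|---|---|---|
| 3 | 3/4 = 0.75 | 4.303 × 3/√3 = 7.45 |
| 6 | 3/7 = 0.43 | 2.571 × 3/√6 = 3.15 |
| 12 | 3/13 = 0.23 | 2.201 × 3/√12 = 1.91 |

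The shifts are well inside the imprecision that such small groups already carry.

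**Check of a replacement.** The groups ≥5.5 to <12, ≥12 to <16 and ≥16 by exact age put every age from 5.5 upward in exactly one group, with no gap and no overlap.

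**The case against.** The best reply is that the upper bound of 16 in the middle group is a slip for under 16. The documents cut at 16 everywhere else, and a programmer would read it that way. That is probably true, but nothing in the SAP says so, and it does not explain the lower bound of 6, which conflicts with eligibility independently.

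A second reply is that the extent of the overlap depends on how age is derived. This is correct: by exact age, a patient aged 16.3 falls only in the upper group. The same convention, however, leaves everyone between 11 and 12 without a group, so it does not rescue the labels.

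Third, the band from 5.5 to under 16 is a recruitment minimum and not an analysis stratum, and the SAP is free to choose other bands. That stands. The defect is the failure to partition; matching the recruitment band is a convenience.

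Fourth, there are safeguards. SAP 4 requires listings by subject. SAP 5 has the trial statistician check outputs for consistency and plausibility. The SAP appendix requires each output to show both the set size and the number contributing, under a separately approved list of outputs. These make an unnoticed error less likely, but none of them defines the groups, and a check on the total can miss an omission and a double count that cancel.

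Finally, the tables are descriptive and no confirmatory inference is planned. That limits the consequence and is reflected in the conclusion.

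**Conclusion.** The point holds. As written, the age groups do not partition the full analysis set under completed years, exact age or rounded age, and nothing elsewhere in either document resolves it.

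The consequence is confined to the descriptive age tables for TABR and SABR. The number of patients affected is unknown and may be zero. One omitted child would be at most 17% of the under-16 patients if the protocol's minimum of 6 is met. One 16-year-old added to the middle group would move its mean by about 0.2 to 0.75 bleeds per year, given assumed group sizes of 12 down to 3 and a rate one SD from the mean. Those shifts are smaller than the groups' own confidence limits, and the overall results do not change. The definition should be corrected because it is a prespecified rule for the primary endpoint that gives wrong counts if followed literally, and it costs almost nothing to put right.

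**What to change.** In SAP 3.4, replace the age groups with mutually exclusive and exhaustive ones that start at the eligibility limit and keep the protocol's cut at 16. State that age is exact age at enrolment. One workable set is ≥5.5 to <12, ≥12 to <16 and ≥16 years; its first two groups then sum to the protocol's paediatric recruitment band. A matching entry for age in SAP 6.1 would settle the derivation.

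The cost is a line of SAP text. It needs no new data and changes no overall analysis.

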4 STATISTICAL ANALYSES

All statistical analyses will be performed using the SAS® software (Version 9.4 or later).

Descriptive statistics will always be given for the entire population.

The analysis of safety will be based on the FAS set.

Analysis of the primary endpoint will be performed on the FAS and PP set.

For secondary endpoints (except endpoints regarding surgeries), FAS and PP analyses will be carried out, unless these analysis sets differ by no more than 5% of patients in the FAS.

Analysis of the efficacy and safety of VCP in surgeries will be based on the SURG set.

If not stated otherwise, the following standard descriptive statistics will be presented:

Descriptive statistics for continuous data

Number of subjects (N), arithmetic mean, standard deviation (SD), minimum, lower quartile, median, upper quartile and maximum will be presented. These descriptive statistics will be determined for measured values and where applicable for differences to baseline.

Descriptive statistics for categorical data

Absolute frequencies (N) will be presented with 0, relative frequencies (%) with 1 decimal. For changes from baseline, shift tables may be generated.

Inferential statistics

Confirmatory statistical inferences are not planned. Any statistical inferences (e.g. confidence intervals) will be of exploratory nature.

All p-values will be rounded to 4 decimals (p<0.0001 will be displayed, if the p-values are less than 0.0001). Unless otherwise specified, statistical significance will be declared if the rounded p-value will be less than 0.05.

All confidence intervals (CI) will be derived two-sided and at a confidence probability of $1-\alpha = 0.95$.

Statistical Analysis Plan	Version 3.0		Page 9 of 17
Sponsor	Octapharma	Protocol No	WIL-29

Listings

All subject data will be listed by subject. Identification variable will be the subject ID (composed of study, center and subject number separated by a hyphen, e.g. '29-01-01'. Any derived data, e.g. TABR, listed will also be stored permanently and will be calculated as outlined in section of this SAP.

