#### 8.5.6.2 Definitions of Surgery Periods and Time Points

- **Preoperative** is defined as the time period of up to 3 hours before the start of surgery.
- The **end of surgery** is defined as the time immediately after the last surgical suture.
- **Postoperative** is the period from the end of surgery to the time the patient returns to on-demand treatment.
- The **end of the postoperative period** is the time the patient returns to on-demand treatment.

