2.2 Deviations from the trial protocol with regard to statistical analyses

For calculation of annualized bleeding rates (ABR) surgery periods will be subtracted from the time period under observation, and bleeding episodes occurred during surgery periods will not be counted as defined in protocol. However, the definition of surgery periods has been clarified. Protocol definition "3 hours before the start of surgery to the time the patient returns to

Statistical Analysis Plan	Version 3.0		Page 7 of 17
Sponsor	Octapharma	Protocol No	WIL-29

on-demand treatment" was updated to "day of surgery until last VCP treatment for surgery". Bleeding episodes that occurred on the day of surgery but before start of surgery will be counted towards the ABR.

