4.7.3 Efficacy in surgical prophylaxis

The assessments will be performed only in non-Croatian centres.

Efficacy in surgical prophylaxis will be analyzed descriptively, presenting summary tables and listings on all aspects of surgical treatment and procedures as well as efficacy ratings.

The following surgery-related parameters will be presented:

- Location, severity (minor or major, for definitions see protocol) and type (planned or emergency) of surgery
- Actual duration of surgical procedure
- Actual blood loss
- Pre-, intra-, and/or postoperative VCP administration data (only listed)
- Pre-, intra-, and postoperative FVIII and VWF & c plasma levels (only listed)
- Details on concomitantly administered products, except standard anesthetic products (only listed)
- Blood transfusion requirements (only listed)
- Assessment of efficacy of surgical prophylaxis at end of postoperative period by treating physician
- Number of successfully treated surgeries ('excellent' or 'good' overall efficacy rating)

Procedures that meet the following criteria are considered as 'major' surgeries. All other procedures are considered 'minor'

- General or spinal anaesthesia required
- Operating into the great body cavities required
- Severe haemorrhage during surgery possible
- Haemostatic therapy for at least 6 days required
- Orthopaedic interventions involving joints (ankle, knee, hip, wrist, elbow, shoulder)
- 3rd molar extraction or extraction of ≥ 3 teeth
- Surgeries/conditions in which the patient's life is at stake

For descriptive statistics on VCP consumption in context of surgeries by time point, all administrations documented under reason for treatment "Surgery" which have been administered before start of surgery will be considered as preoperative and administered between start and end of surgery as intraoperative treatments. Post-operative treatments will include all VCP treatments documented under reason for treatment "Prophylaxis after surgery".

Statistical Analysis Plan	Version 3.0		Page 13 of 17
Sponsor	Octapharma	Protocol No	WIL-29

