4.8 Safety

All safety analyses will be based on the FAS population.

The analysis of safety will include the occurrence of Adverse Drug Reactions and the occurrence of VWF/FVIII inhibitors.

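### The SAP gives two analysis sets for surgical safety, and the SURG set, built for effectiveness of prophylaxis, does not fit a safety summary (minor)

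*SAP*

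**What the plan says.** SAP section 4 first gives a general rule, "The analysis of safety will be based on the FAS set", and a few lines later a rule for surgery: "Analysis of the efficacy and safety of VCP in surgeries will be based on the SURG set". SAP 4.8 returns to safety and says "All safety analyses will be based on the FAS population". The FAS "will include all enrolled subjects" (SAP 3.1). The SURG set is a subset of it, "containing all subjects who underwent a surgical procedure treated with any VCP prior to start of surgery" (SAP 3.3).

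SAP 4.8.1 defines treatment-emergent ADRs (TEADRs) as those starting or worsening after VCP infusion begins, and it describes no table or listing by surgery. SAP 4.7.3, on surgical efficacy, lists no ADR item, but it does summarise VCP given before, during and after the operation. Postoperative doses are identified by the reason 'Prophylaxis after surgery'.

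Surgery timing is defined in several places. In Protocol 8.5.6.2, preoperative "is defined as the time period of up to 3 hours before the start of surgery", and the postoperative period ends when the patient returns to on-demand treatment. SAP 2.2 replaces this, for the bleeding rates, by the span from the day of surgery to the last VCP treatment for surgery. SAP 6.1 turns that span into a formula.

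**The concern.** The plan announces a safety analysis in surgeries, assigns it to one set, then assigns every safety analysis to another without saying how the two fit together. A programmer working from 4.8 would have no instruction to produce a surgical summary. One working from section 4 would use a set designed for a different question.

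For effectiveness of surgical prophylaxis, it is reasonable to require VCP before the operation. For safety, what counts is exposure to VCP around the operation, whenever it was given. The protocol asks for any surgery to be documented, records emergency surgery as a type, includes ADR monitoring in its surgical flow chart (Table 6), and names thromboembolic events among medically important serious reactions (10.1.1). A surgical safety summary is therefore worth having only if its denominator is the exposed patients and its events can be tied to an operation.

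**Working it through.** The point concerns wording and definitions, and no figure in the plan bears on it. The SAP's one precision statement, ± 0.8 for the mean ABR, reproduces (1.96 × 3/√55 = 0.793) but is unrelated.

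**1. The two rules.** Section 4 alone can be read as a general rule (FAS) with a surgical addition (SURG). Section 4.8 then covers all safety analyses and makes no exception. The conflict is real on the text, and one sentence would resolve it.

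**2. Who is in SURG.** Take the pre-dose in SAP 3.3 to mean a dose given for the operation, and list every pattern with at least one perioperative dose:

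| Before | During | After | In SURG |
|---|---|---|---|
| yes | no | no | yes |
| yes | yes | no | yes |
| yes | no | yes | yes |
| yes | yes | yes | yes |
| no | yes | no | no |
| no | no | yes | no |
| no | yes | yes | no |

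Four of the seven patterns are kept and three are dropped, although SAP 4.7.3 summarises intraoperative and postoperative doses. This counts patterns, not patients. The documents give neither the number of surgeries nor the share without a preoperative dose.

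**3. The pre-dose itself.** SAP 3.3 requires any VCP before the start of surgery, with no purpose and no earliest time. Read literally, an on-demand dose for an unrelated bleed weeks earlier would qualify a subject, even one whose operation was not covered by VCP at all. The protocol's limit of 3 hours is not carried into the definition. Two programmers could therefore build different SURG sets.

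**4. Linking a reaction to an operation.** SURG selects subjects, not periods. The TEADR definition has no surgical window. The surgery period in SAP 2.2 and 6.1 is used for bleeding rates, and the dose categories in SAP 4.7.3 for consumption. None is attached to ADRs.

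**5. The surgery period as computed.** SAP 6.1 takes the date of surgery minus the date of the last surgical treatment, plus 1, divided by 365.25. Its own general rule for durations is later date minus earlier date plus 1. As an illustration, suppose the last surgical dose is 6 days after the operation:

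- As written: (0 − 6 + 1)/365.25 = −5/365.25 = −0.0137 years.
- By the general rule: (6 − 0 + 1)/365.25 = 7/365.25 = 0.0192 years.

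The formula is right only when surgery and last dose fall on the same day. It needs correcting before it is used as a safety window.

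**The case against.** The strongest reply is that this is mostly wording. Section 4 gives a general rule and then a specific one, SURG is a subset of the FAS, and 4.8 may only be restating the general rule. The protocol's surgical objective and endpoint concern effectiveness, while its safety endpoint is ADRs throughout the study. A preoperative dose suits a prophylaxis set, since Table 6 marks only the administration within 3 hours before surgery as non-optional. Most of this stands. It lowers the weight of the point, but it does not remove the unqualified sentence in 4.8 or make SURG an exposure-based set.

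Three stronger readings are tempting and are not supported:

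- A reader might infer that no surgical safety result will be produced. The full list of outputs is a separate document that is not part of this SAP, so silence in the SAP text does not show that.
- A reader might infer that reactions go unreported. Omitted subjects remain in the FAS. Their TEADRs are tabulated, ADRs after first VCP are listed, and serious, fatal and discontinuation cases have their own listing (SAP 4.8.1).
- A reader might infer that a summary on SURG would consist mostly of non-surgical reactions, because an operation takes up a small part of 6 months. No passage says that the whole follow-up will be counted as surgical. Calendar share also does not measure the share of reactions, because TEADRs are tied to infusions and on-demand dosing is intermittent.

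**Conclusion.** The point holds as a minor one. The SAP names two sets for surgical safety without reconciling them. If SURG is used, it is the wrong basis for safety in three respects: it can omit subjects exposed only during or after the operation, it leaves the qualifying dose undefined in purpose and time, and it has no link between a reaction and an operation.

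The effect is limited to the surgical summary. Overall safety on the FAS is unaffected. The study is descriptive with no confirmatory inference, so no error rate or power is involved. How many patients would be omitted cannot be computed from the documents. The omission rests on reading the pre-dose as one given for the operation. On the literal reading some of these patients enter through an unrelated earlier dose, which makes membership arbitrary instead.

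**What to change.** - Keep SURG for effectiveness of surgical prophylaxis, and state in SAP 3.3 the purpose and timing of the qualifying dose.
- In SAP 4 and 4.8, state that overall safety uses the FAS and that the surgical safety summary is additional to it.
- Base that summary on every subject with any VCP recorded under 'Surgery' or 'Prophylaxis after surgery', whether given before, during or after the procedure.
- Show TEADRs with onset within the surgery period separately from those with later onset, so that ending the window at the last surgical dose does not hide a delayed reaction. Give the numbers of surgeries and of subjects.
- Reconcile the surgery-period definitions in Protocol 8.5.6.2, SAP 2.2 and SAP 6.1 into one for analysis. It should say whether doses coded 'Prophylaxis after surgery' extend the period and how a preoperative dose before the day of surgery is handled. Correct the date order in the SAP 6.1 formula.

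The cost is a few SAP sentences, one corrected formula and one table, built from surgery dates, ADR onset dates and reason for injection, all already recorded. The table will probably be sparse, and is best read beside the individual listings.
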